ADVANCES IN MECHANISMS Advances in understanding the role of cutaneous HCQ deposes acquired after prolonged previous treatment in maintaining drug-induced TLRs-7 and -9 inhibition would justify reducing the therapeutic dose based on the drug's immunomodulatory mechanisms of action.

SAMPLE SIZE

The sample size was calculated based on the difference in Reactivation of SLE/SJS in one year after the removal or maintenance of hydroxychloroquine, as observed in the study by Tsakonas et al., 1998 and assuming: 95% confidence interval, α error of 5%; power of 80%; expected success rate after 1 year in the group that kept HCQ at the standard dose (Tsakonas et al., 1998)- 84%; expected success rate after 1 year in the group that fully removes HCQ (Tsakonas et al., 1998)- 59%; no-inferiority margin- 50% of the difference between maintaining chloroquine or removing it completely, i.e., delta of 12%; losses- 10%; n in each group- 128; total number of patients to be recruited: 256 (for SLE/JSLE).

statistical analysis The comparison of the risk of inflammatory activity of the disease in patients using standard dose (HCQ 400 mg/day) vs. patients with reduced dose (HCQ 400mg/day - 3X week) will be made through a survival curve by the log-rank test. The categorical variables will be evaluated by fisher's exact or chi-square test and quantitative variables by student and mann-whitney t tests, when applicable.

TITLE OF THE SUBPROJECT 1C

Prospective study of the pharmacokinetics of hydroxychloroquine in patients with Systemic Lupus Erythematosus using attack dose diseases SLE and JSLE.

Justification

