- Evaluate the clinical/laboratory response and adverse events in both groups.
- Verify a possible correlation of HCQ concentrations in blood and saliva with interferon-alpha and TNF production levels by plasmacytoid dendritic cells and disease activity parameters.
- Correlate blood and salivary levels of HCQ and its metabolites in Patients with SLE with adherence to this treatment.

NUMBER OF INDIVIDUALS

Total patients needed for the study = 96 (SLE).

STUDY DESIGN

Prospective randomized study controlled for a period of six months of patients with SLE who will start the use of HCQ.

Patients will be randomized randomly into two groups: traditional group - without increasing the daily dose (HCQ 400 mg/day); attack dose group - with increased daily dose (HCQ 800 mg/day for 6 months). Patients will be evaluated for the activity of the underlying disease in a "blind" way. HCQ concentrations will be assessed at the entrance and at the end of the study.

The groups will be compared for episodes of disease activity (clinical and laboratory parameters), inflammatory cytokines, and expression of TLR-7 and TLR-9 receptors.

Blood concentrations of HCQ and metabolites will be determined in both groups by HPLC (Munster et al., 2002).

The following indexes will be used to assess disease activity:

- SLE: SLEDAI-2K (Gladman et al., 2002) and active disease randomly defined as SLEDAI-2K \geq 6.

- Renal activity: BP, urine type I, protein and creatinine in an isolated urine sample, serum creatinine, C3, C4, anti-dsDNA, according to the ACR Guidelines (Hahn et al., 2012).

Adherence will be assessed by the MASRI questionnaire applied by a pharmacist not directly involved in patient care (Koneru et al., 2007).

The following clinical, laboratory and treatment data will be evaluated in the groups (traditional dose and attack dose): age, sex, race, weight, height, BMI, ideal weight; disease time, time of HCQ use, adherence to treatment; smoking; use and dose of prednisone, methotrexate, azathioprine, mycophenolate mofetil, cyclophosphamide, non-hormonal anti-inflammatory drugs; urinary protein/creatinine ratio; serum creatinine; HCQ blood concentrations by HPLC MS/MS; general- gastrointestinal and cutaneous adverse events.

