The sample size was calculated considering that the faster the 1000 ng/mL blood level is reached, the greater the improvement in lupus activity and the lower the recurrence rate in the groups is observed, 6 months after the onset of HCQ treatment. In the study by Tett et al., 2000, in patients with AR, in the group that started HCQ at a dose of 400 mg/d, the mean seric level was 870.3 ± 329.3 ng/mL, that is, about 34% of patients reached > 1000 ng/mL blood level after 6 months. It is estimated that more than 20% of patients will reach this value with twice the attack dose, we calculate (based on: 95% confidence interval, error α 5%; power of 80%) expected frequency of patients with 1000 ng/mL > level after 6 months in the 400 mg/d group: 34%; expected frequency of patients with 1000 ng/mL > level after 6 months in the 800 mg/d group: 55 %; losses: 10%; n = 96.

STATISTICAL PLAN

The comparison of the time required to reach the level of 1000 ng/mL of HCQ in patients with SLE and JSLE, using survival curve by log-rank test. Categorical variables will be evaluated by Fisher's exact or chi-square test and quantitative variables by Student and Mann-Whitney *t* tests, when applicable.

Project 2: THALIDOMIDE

EVALUATION OF THE TREATMENT OF CUTANEOUS LUPUS ERYTHEMATOSUS WITH THALIDOMIDE: CLINICAL, LABORATORY AND HISTOLOGICAL FACTORS ASSOCIATED WITH CLINIC RESPONSE AND ADVERSE EFFECTS

Diseases

Systemic lupus erythematosus with cutaneous involvement (LEC).

Justification

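### Subproject 1C: 96 patients in total cannot give 80% power for 34% versus 55%; power is about 50 to 55%, and 96 matches the number needed per group

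*Combined protocol and SAP*

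**What the plan says.** Subproject 1C is a two-arm trial. Its study design section states: "Prospective randomized study controlled for a period of six months of patients with SLE who will start the use of HCQ". It continues: "Patients will be randomized randomly into two groups: traditional group - without increasing the daily dose", with the second group receiving the attack dose. The allocation ratio is not given.

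The size appears in two places:

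- **Number of individuals:** "Total patients needed for the study = 96 (SLE". Here 96 is explicitly a total.
- **Sample size:** the calculation is "based on: 95% confidence interval, error α 5%; power of 80"%. The expected proportions above 1000 ng/mL are "level after 6 months in the 400 mg/d group: 34"% and "level after 6 months in the 800 mg/d group: 55"%. With 10% losses it ends in an unlabelled 96: "level after 6 months in the 800 mg/d group: 55 %; losses: 10%; n = 96".

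No other section gives a different total for 1C. Subproject 1B, by contrast, labels both of its figures: "n in each group- 128; total number of patients to be recruited: 256 (for SLE/JSLE".

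**The concern.** For 34% versus 55% at 80% power, 48 patients per arm looks too few by about half. 1B states a number per group and doubles it. 1C gives a single unlabelled figure, which is then used as the total. That pattern suggests a per-group result was carried over without doubling.

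At stake is the power of the primary comparison in a randomised trial. The protocol puts the risk of missing the assumed effect at 20%. If 96 is recruited in total, that risk is about one in two. A non-significant result would then say little about whether the higher dose brings more patients to the target level.

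**Working it through.** **Inputs** (Subproject 1C, sample size): p1 = 0.34, p2 = 0.55, alpha 0.05, power 0.80, losses 10%. Two inputs are assumed because the protocol does not state them: a two-sided test (suggested by the 95% confidence interval) and 1:1 allocation.

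**Step 1. Reproduce 96.** The pooled two-proportion formula, per group, is

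n = [z(0.975)·√(2·p̄·q̄) + z(0.80)·√(p1q1 + p2q2)]² / (p2 − p1)²

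- p̄ = 0.445, so √(2 × 0.445 × 0.555) = 0.7028
- √(0.34 × 0.66 + 0.55 × 0.45) = √0.4719 = 0.6870
- n = (1.960 × 0.7028 + 0.8416 × 0.6870)² / 0.21² = 3.8246 / 0.0441 = 86.7, so **87 per group**
- Losses added as 10%: 87 × 1.10 = 95.7, so **96 per group, 192 in total**
- Losses by division: 87 / 0.90 = 96.7, so 97 per group, 194 in total

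The stated 96 is therefore recovered as a number per group.

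**Step 2. Check the convention against 1B.** With 84% success, a 12-point margin, one-sided 5% and 80% power, n = (1.645 + 0.8416)² × 2 × 0.84 × 0.16 / 0.12² = 115.4, so 116. Then 116 × 1.10 = 127.6, so 128, which is the figure 1B gives for each group and doubles to 256. The same steps in 1C give 96 per group.

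**Step 3. Look for any route to 96 as a total.**

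| Method | Per group before losses | Total with losses (÷ 0.90) |
|---|---|---|
| Pooled, two-sided | 87 | 194 |
| Continuity-corrected, two-sided | 97 | 216 |
| Unpooled, two-sided | 84.0 | about 187 |
| Pooled, one-sided 5% | 69 | 154 |
| Log-rank, two-sided (Schoenfeld to Freedman) | 83 to 89 | about 185 to 197 |
| Log-rank, one-sided (Schoenfeld) | 65 | about 145 |

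The log-rank rows use a hazard ratio of ln(0.45)/ln(0.66) = 1.92 and an average event probability of 0.445. None comes near 96.

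**Step 4. Power with 96 in total.** For n per group, power = Φ{[0.21·√n − 1.960 × 0.7028] / 0.6870}.

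- No losses, n = 48: (1.4549 − 1.3775) / 0.6870 = 0.113, power **54.5%**
- After 10% losses, n = 43: (1.3771 − 1.3775) / 0.6870 = −0.001, power **50.0%**

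| Test | 48 per group | 43 per group |
|---|---|---|
| Normal approximation, two-sided | 54.5% | 50.0% |
| Exact power of the chi-square test | 55% | 51% |
| Log-rank (Schoenfeld) | 57% | 53% |
| Fisher's exact (secondary) | 47% | 41% |
| Normal approximation, one-sided 5% | 67% | 63% |

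**Step 5. What 96 in total can detect.** Solving the same power formula for p2 at 80% gives 62.2% with 48 per group and 63.8% with 43 per group. These are differences of 28 and 30 points, where the plan assumes 21.

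**The case against.** The strongest counter-argument is that nothing in the protocol calls 96 the number per group. That reading is inferred from a numerical match, and the match is not unique: dividing by 0.90 gives 97, and 34% versus 54% gives 96 per group before any losses. 1B is a different, non-inferiority design, so its labelling is supporting evidence and not proof. This stands as a limit on explaining how the error arose. It does not rescue the plan, because 96 as a total fails under every two-group calculation tried.

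Sidedness and allocation are also unstated. A one-sided 5% test would raise power to 63 to 67%, which still falls short of 80%.

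The planned primary analysis is a log-rank test on time to 1000 ng/mL; Fisher's exact and chi-square tests are assigned to categorical variables. The 41% and 47% for Fisher's test are therefore secondary. The log-rank figures, 53 to 57%, lead to the same conclusion. They could hardly be much better: the study design section measures concentrations only at entry and at the end of the study, so the comparison is close to one of two proportions at 6 months.

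Finally, the two sections do not disagree on the number, since both say 96. The fault is that 96 as a total does not follow from the inputs given for it.

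**Conclusion.** The concern holds. On the protocol's own inputs, 96 patients in total give two-sided power of 54.5% with no losses and 50.0% after the planned 10% losses, a shortfall of about 25 to 30 points from the stated 80%. This assumes 1:1 allocation and a two-sided 5% test. The shortfall remains with a one-sided test and with the log-rank test. That 96 was meant per group is very likely but inferred; the conclusion does not depend on it. The correction is necessary because the misstatement concerns the power of the primary comparison.

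**What to change.** Make the number of individuals and the sample-size section of Subproject 1C consistent with the stated power, and label the figure. Either of these would do:

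1. **Keep 96 in total and restate the power.** For example: with 96 patients randomised 1:1 (about 43 evaluable per group after 10% losses), a two-sided 5% test has about 50% power for 34% versus 55% (54% with no losses), and 80% power only for 34% versus about 64%.
2. **Label 96 as the number per group and give 192 as the total.** About 86 to 87 evaluable per group then gives 79.7 to 80.1% power.

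In both cases, state the allocation ratio and whether the test is one- or two-sided. Option 1 changes text only, though it shows a much weaker trial. Option 2 doubles recruitment and is not needed to correct the error.

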- The possible combination of plasma levels of TNF-, α IFN-1, BAFF (B-cell activator factor) and thalidomide levels in the blood and saliva with the therapeutic response and the adverse effects.

Secondary:

- Evaluate the possible association between TNF-levels, adjoin molecules, apoptosis markers and growth factors in skin biopsy samples with efficacy and adverse effects.

- Evaluate the presence of fine fiber neuropathy in skin biopsy specimens.

- Establishment of a pharmacokinetic-pharmacodynamic model of thalidomide dose reduction in patients with SLE.

NUMBER OF INDIVIDUALS

40 patients with lupus (SLE) and active cutaneous involvement will be included.

STUDY DESIGN

A prospective study for a period of 12 months with adult patients with SLE (according to the classification criteria of the American College of Rheumatology- ACR) (Hochberg, 1997) with active skin lesions at the entrance regardless the use of hydroxychloroquine and/or dapsone and/or prednisone and/or immunosuppressants, and who are eligible for the use of thalidomide (see inclusion criteria) (Ministry of Health, 2013; System for Thalidomide Education and Prescribing Safety, Zeldis et al., 1999).

The initial dose of thalidomide will be 100 mg/day for 3 months and reduced to 50 mg/day and 25 mg/day, at any time depending on the therapeutic response until complete 12 months of treatment.

All patients will be treated simultaneously with hydroxychloroquine, unless there is contraindication for use of this medication.

The other drugs used for SLE control will be maintained during the study, including prednisone (with subsequent gradual dose decrease in case of improvement of skin lesions).

Patients will be clinically evaluated at baseline, then 1 month, 6 months and 12 months after inclusion for:

- the global activity of the disease through the SLEDAI-2K (Systemic Lupus Erythematosus Disease Activity Index 2000) (Gladman et al., 2002);

- the index of activity and skin severity (CLASI) (Albrecht et al., 2005);

- possible adverse effects and adherence by the Medication Adherence Self-report Inventory (MASRI) applied by a pharmacist not directly involved in patient care (Koneru et al., 2007);

- quality of life by the visual analog scale and the SF36 questionnaire (Mosca et al., 2010).

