Plasma levels of TNF-, IFN-1, BAFF, transforming growth factor-beta (TGF- β) and thalidomide levels in the blood and saliva will be performed at zero time, at 30 days, 3 months, 6 months, 9 months and 12 months.

The clinical evaluation of peripheral neuropathy will be performed at each consultation by anamnesis and through THE ENMG at baseline, at 6 months and at 12 months.

Skin biopsy of an active lesion will be performed at baseline for histological evaluation, including the study of immunohistochemistry expression of TNF-, TGF $\alpha\beta$ (Kuhn et al., 2010; Yu et al., 2013) and plasmacytoid and pro-apoptotic dendritic cell markers such as caspase 3, CD25, CD35, CD21, CD36, CD68, CD31, detection of IgG, IgM, C3 and T and B cell markers (Bălănescu et al., 2010).

Skin biopsies of uninjured skin will be obtained from the thigh area, at baseline and at 6 months for the fine fiber neuropathy assessment through immunostaining with PGP 9.5 (Birnbau & Bingham, 2014).

- Pharmacokinetic-pharmacodynamic model of use of thalidomide will be performed in two groups of 5 patients with different doses (50 mg/day and 100 mg/day).

Outcomes: evaluations on days 0 and 30.

a) Improvement in skin symptoms and severity scores [(Cutaneous Lupus Area and Severity Activity Index score (CLASI)]. Change in CLASI score assessing the activity/severity criteria from 0 to 70 will be performed. The reduction represents an improvement in skin injury related to lupus in terms of activity and/or severity. CLASI evaluates erythema and scar/hypertrophy/atrophy in 13 anatomical areas. Membrane lesions and alopecia are also part of this index.

b) Cytokine dosage. Plasma levels of TNF- α and IFN-1 will be determined by Luminex MAP (EMD Millipore Corporation®). Plasma samples will be stored at -80oC until use.

TARGET POPULATION

Inclusion criteria:

- Adult patients with SLE (according to the classification criteria of the American College of Rheumatology) (Hochberg, 1997) with active skin lesions at the entrance to the research despite the use of hydroxychloroquine and/or prednisone and/or immunosuppressants who are eligible for thalidomide use.

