Histological sections submitted to immunohistochemistry techniques to demonstrate cellular and cytokine elements will be digitized by the Panoramic Scan (3D Histech, Hungary) scanner to obtain virtual histological slides. The reading of the material and capture of the images to be analyzed will be carried out with the program Panoramic Viewer version 1.15.2.21080 (3D Histech, Budapest, Hungary). The quantification of immune tagged cellular elements will be performed with the aid of image analysis program Image Pro Plus version 4.5.0.29 (MediaCybernetics Inc. , Rockville, MD, USA).

The quantification of fine nerve fibers will be performed by counting intraepidermal nerve fibers per millimeter of dermal epidermal junction and the relationship between area of marked subepidermal nerve fibers and total area of papillary dermis examined (Rodrigues Júnior, 2011).

Safety

Patients who fit the safety recommendations of the Ministry of Health will be included.

Clinical (with special attention to symptoms of peripheral polyneuropathy) and laboratory of adverse effects (including leukocyte count) will be performed at the entrance into the study and each medical consultation.

The ENMG will be performed to include in the study, at 6 months and at the end of the study.

If there is no clinical response within 2 months of the use of thalidomide, or in the clinical suspicion or enmg of peripheral neuropathy at any time, thalidomide will be suspended (out of the study) and follow-up of the patient will be continued in the outpatient clinics of the Rheumatology and Dermatology Services of HC-FMUSP.

WITHDRAWALS

See item Security.

ORIGINALITY WITH CARE IMPACT

There are no studies correlating tissue expression of cytokines with blood and salivary levels of thalidomide and its possible role as a predictor of response and adverse effects in patients in skin lesions of SLE. In addition, there are no studies on the value of skin biopsy in the diagnosis of thalidomide-induced neuropathy.

The expected impact with the availability of blood and salivary dosage of thalidomide in clinical practice is that this parameter may be a predictor of clinical response and neuropathy.

ADVANCES IN MECHANISM

The expected advance is a better understanding of the role of thalidomide in the expression of cytokines in the cutaneous lesion of SLE.

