In addition, we hope to determine whether the mechanism of thalidomide-induced neuropathy would target thin nerve fiber injury to histological skin analysis of patients treated with this medication.

SAMPLE SIZE

This is a convenience sample.

STATISTICAL PLAN

Patients with vs. without therapeutic response to thalidomide and vs. without signs of peripheral polyneuropathy will be compared for categorical variables by fisher's exact or chi-square test and, as for

quantitative variables, by t-Student or Mann-Whitney tests, when applicable. The influence of the different variables on disease activity and polyneuropathy will be evaluated by multivariate analysis.

References

- Ackerman, AB. Histologic diagnosis of inflammatory skin diseases. Philadelphia, Lea & Febiger, 1978. P. 813.
- Agency for Healthcare Research and Quality. Priority Areas for National Action: Transforming Health Care Quality. Rockville, MD: Agency for Healthcare Research and Quality; 2003.
- Bernstein HN. Ocular safety of hydroxychloroquine. *Ann Ophthalmol.* 1991;23(8):292-6.

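### Project 2: thalidomide dose falls with response, so any responder comparison using post-reduction drug levels is biased; the plan does not fix which level is used or account for dose at sampling

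*Combined protocol and SAP*

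**What the plan says.** All places are in Project 2 of the combined protocol and SAP.

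- **Primary objective:** it concerns "thalidomide levels in the blood and saliva with the therapeutic response and the adverse effects", alongside plasma cytokines.
- **Study design, dose:** "The initial dose of thalidomide will be 100 mg/day for 3 months", and in the same sentence it is "reduced to 50 mg/day and 25 mg/day, at any time depending on the therapeutic response", over 12 months of treatment.
- **Study design, sampling:** levels are "performed at zero time, at 30 days, 3 months, 6 months, 9 months and 12 months".
- **Study design, clinical visits:** "Patients will be clinically evaluated at baseline, then 1 month, 6 months and 12 months after inclusion". CLASI and SLEDAI-2K are scored then.
- **Safety:** "If there is no clinical response within 2 months of the use of thalidomide", the drug is suspended and the patient leaves the study. Suspected neuropathy has the same consequence.
- **Statistical plan:** "Patients with vs. without therapeutic response to thalidomide and vs. without signs of peripheral polyneuropathy will be compared", using t or Mann-Whitney tests for quantitative variables. A multivariate analysis of disease activity and polyneuropathy follows, with no covariates listed.
- **Sample size:** 40 patients, described as a convenience sample.

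The plan does not define response, give it a time point, choose a visit for the drug level, or mention the dose at sampling.

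**The concern.** Response lowers the dose, and dose drives the level. A patient who does well contributes samples taken at 50 or 25 mg/day. A patient stopped for non-response by 2 months has one scheduled on-treatment sample, at day 30, on the starting dose. A visit mean, a last level or pooled levels would therefore set reduced-dose samples in responders against starting-dose samples in early non-responders. Low levels in responders would then be a consequence of response, not evidence about what predicts it.

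The section on originality and care impact expects the blood and salivary level to serve as a predictor of clinical response and neuropathy. If post-reduction levels enter the comparison, a useless level could look inversely predictive and a useful one could look uninformative.

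**Working it through.** The plan gives no figure to reproduce: the sample size has no power, effect size or SD.

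**Inputs from the documents.** 40 patients; doses of 100, 50 and 25 mg/day; five on-treatment draws (30 days, 3, 6, 9 and 12 months); exit at 2 months without response. For the split, the retrospective study cited in the justification had 81% partial or complete response: 40 × 0.81 = 32.4, so about 32 v 8.

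**Assumptions not in the documents.** Level proportional to dose; lognormal levels with between-patient CV of 40% or 60%; the taper patterns below; non-responders sampled once, at 100 mg/day.

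**Step 1, break-even.** Observed ratio (responder / non-responder) = true equal-dose ratio × responder dose / 100. The direction reverses when the true ratio is below 100 / responder dose.

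- Level at 50 mg/day: 100/50 = 2.0.
- Level at 25 mg/day: 100/25 = 4.0.
- Mean over 100, 100, 50, 50, 25 (mean dose 325/5 = 65): 100/65 = 1.54.
- Mean over 100, 100, 100, 50, 50 (mean dose 400/5 = 80): 100/80 = 1.25.

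**Step 2, no true relation.** Two-sided Mann-Whitney at 5%, 32 v 8, 4,000 simulated trials per setting. The last two columns give the share of trials with significantly lower levels in responders.

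| Responder level used | Median ratio | CV 40% | CV 60% |
|---|---|---|---|
| Mean over 100, 100, 50, 50, 25; all tapered | 0.65 | 75% | 45% |
| Mean over 100, 100, 100, 50, 50; all tapered | 0.80 | 26% | 15% |
| First pattern, but half of responders tapered | about 0.80 | 20% | 13% |
| Single level at 50 mg/day | about 0.50 | 99% | 84% |
| Single level at 25 mg/day | 0.25 | 100% | 100% |
| Day-30 level, all at 100 mg/day | about 1.0 | 2% | 2% |

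The day-30 row also shows 2–3% significantly higher, so its total error is about the nominal 5%. The split matters: at CV 40% the first row becomes 49% with 36 v 4 and 90% with 24 v 16. A second model added visit-to-visit variation (log-SD 0.25, total CV about 41% or 61%) and let the split vary at random around 81%. It gave 82% / 56% for a faster taper (100, 100, 50, 25, 25), 56% / 29% for 100, 100, 50, 50, 50, and 96% / 77% for a level at 50 mg/day.

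**Step 3, true ratio 1.5 (higher levels in responders).**

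- Mean dose 65: expected ratio 1.5 × 0.65 = 0.98. The relation is cancelled, with a significant reversal in about 3%.
- Mean dose 80: 1.5 × 0.80 = 1.20. The relation is attenuated; the correct finding appears in 19% / 11% (CV 40% / 60%).
- Level at 50 mg/day: 1.5 × 0.50 = 0.75, with a significant reversal in 42% / 23%.
- Day-30 level: ratio about 1.5, with the correct finding in 70% / 40% and essentially no reversals.

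**The case against.** The strongest reply is that the plan never commits to a biased comparison. The statistical plan labels no analysis primary, does not mention averaging, and gives generic tests for quantitative variables. Levels are drawn at fixed visits, so a visit-by-visit comparison is at least as natural, and at day 30 the dose is common. This stands. The fault is an exposure left open in a design where several obvious choices are biased; it is not a biased analysis written down. But nothing points to day 30, and the justification wants longitudinal evaluation of concentration to monitor efficacy, which makes use of later levels likely. Visit-by-visit comparison is also no way out at 6–12 months, because early non-responders have left by then.

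The multivariate sentence does not repair this: it names no dose or time term. Nor do the PK-PD groups, which are two sets of 5 patients assessed at days 0 and 30.

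Two further points stand. The simulated percentages depend on a taper schedule the plan does not give, and milder tapers bring the visit-mean figure down to 13–26%. And a reader might infer that every level in a non-responder comes from 100 mg/day. The documents do not support that: response is undefined, so a patient who improves, is reduced and then relapses could be counted as a non-responder with reduced-dose levels.

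**Conclusion.** The point holds for any comparison that includes levels drawn after a response-driven reduction, and nothing in the plan excludes such a comparison. The direction of the bias follows from the design. The break-even ratios (2 at 50 mg/day, 4 at 25 mg/day) rest only on dose proportionality. The false-finding rates (roughly 13–75% for visit means with 32 v 8, higher with a faster taper or a more even split; 84–99% for a level at 50 mg/day) also rest on the assumed CV, taper and split. The day-30 level is free of the problem, and so is the 3-month level if the starting dose really is fixed for 3 months.

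Two stronger readings are not supported. One is that a true positive relation would generally be reversed: for visit means a true ratio of 1.5 is mostly attenuated or cancelled, and outright reversal is mainly a risk for single late levels. The other is that the neuropathy comparison has the same reverse causation. Reduction is driven by therapeutic response and the drug is suspended on suspicion of neuropathy, so the issue there is exposure misclassification: a late level after a taper understates the exposure that came before the nerve finding. That part is reasoned, not simulated.

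This should be fixed, but in a 40-patient convenience sample exploring a possible association it does not undermine the study as a whole.

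**What to change.** In the Project 2 statistical plan:

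1. Name the day-30 level as the exposure for the level-response comparison. Flag patients already reduced by day 30 and repeat the comparison without them.
2. Define response on CLASI at a stated later time point, for example the scheduled 6-month evaluation. Count patients stopped at 2 months for no response as non-responders. No clinical evaluation is scheduled at 2 months, so state how that judgement is recorded.
3. Record the dose at every draw. Analyse later levels only as secondary: divided by dose at sampling and drawn before the outcome, or in a time-varying model that includes current dose.
4. For neuropathy, use cumulative dose and levels drawn before the first sign.
5. Reconcile the two parts of the dosing sentence in the study design, which sets a 3-month starting period and also allows reduction at any time. How far the 3-month level can be trusted depends on this. No change to dosing is proposed.

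The cost is a few sentences and one recorded field per sample, with no extra draws. The downside is that the main comparison uses one level per patient, with power of about 70% (CV 40%) to 40% (CV 60%) for a true ratio of 1.5.
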